11. EVALUATION OF EXPLORATORY OUTCOME MEASURES

11.1 TGA Parameters Over 72 Hours

The analysis of TGA parameters over 72 hours will be performed on the PKFAS.

TGA parameters will be plotted against time for each subject. In addition, TGA parameters will be summarized using descriptive statistics at each time point.

11.2 TGA Parameters Pre- and Post- Infusion

Analysis of TGA parameters pre- and post- infusion will be performed on the FAS.

TGA parameters will be summarized using descriptive statistics for exposure day 1 (only applicable for newly recruited subjects) as well as for end of study.

In addition, percent changes from pre-infusion time-point will be summarized for exposure day 1 as well as for end of study.

The percent change in TGA parameters will be calculated as:

$((tga2-tga1)/tga1)*100$,

where tga1 denotes the TGA value at the pre-infusion time-point and tg2 denotes the post-infusion TGA value.

These tables will be created for the on-demand treatment only (i.e. subjects who received on-demand treatment exclusively over the whole study period), for the overall prophylaxis (combined standard, modified and PK-tailored prophylaxis) only, for subjects who received on-demand treatment and any prophylaxis treatment (i.e. subjects who switched during the study) as well as for all treatment regimens together.

Additionally, percent changes from exposure day 1 to end of study will be summarized for newly recruited subjects.

The association of pre-infusion TGA parameters with pre-infusion FIX activity level during prophylaxis will be explored. Scatterplots of pre-infusion TGA parameters against pre-infusion FIX level will be presented for each time point.

In addition, the median pre-infusion TGA parameter against median FIX level for each subject will be presented if pre-infusion values of FIX level and TGA parameters are similar across all time-points. To determine the suitability of this analysis, a plot of individual and median pre-infusion TGA parameter values by subject will be provided. A similar plot will also be produced for pre-infusion FIX activity level at the corresponding time-points.

The association of pre-infusion TGA parameters with spontaneous bleeds during prophylaxis will be explored. This will be done using box plots of the pre-infusion TGA parameter values for subjects who did and who did not experience one or more spontaneous bleeds within 4 weeks after the corresponding pre-infusion TGA sample.

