#### **8.1.4 Additional Blood Sampling for Determination of FIX Activity and TGA Parameters**

Additional blood sampling for FIX activity and TGA determination will be performed in approximately 40 subjects  $\geq 12$  years of age **without requiring a wash-out period** (see Section 11.1 and Section 11.2 for further details).

In approximately 20 subjects receiving twice weekly standard prophylactic infusions of BAX326, pre- and post-infusion TGA parameters concurrent with IR for FIX will be determined over 6 months at their regular 3-monthly visit. Also, at 4 additional different time points within this 6-month period, pre- and post-infusion TGA parameters and FIX activity level will be determined. On 2 occasions these should be assessed 3 days after a prophylactic infusion of BAX326 (ie, before and after the subsequent prophylactic infusion of BAX326), and on the other 2 occasions 4 days after a prophylactic infusion of BAX326 (ie, before and after the subsequent prophylactic infusion of BAX326 (Table 11.1-4)).

For subjects receiving modified prophylaxis, FIX acitivity levels and TGA parameters will also be determined within a 6-month period pre- and post-infusion at 4 different timepoints. The pre- and post-infusion blood draws should occur such that they reflect the dosing interval.

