#### **14.3.3 Exploratory Outcome Measures**

TGA parameters (lag time, time to peak thrombin generation, peak thrombin generation, and ETP) will be summarized using descriptive statistics and displayed graphically.

The association of pre-infusion TGA parameters with pre-infusion FIX activity level and spontaneous bleeds during prophylaxis will be explored.

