**At regular 3-month study visit:**

- Initially, ie, at start of the 6-month period
- after 3 months  $\pm$  1 week and
- after 6 months  $\pm$  1 week of twice-weekly prophylactic infusions

According to the requirements of the 3-month study visits, there will be a wash-out period of at least 5 days (120 h), preferably 7 days. Concurrent with the determination of FIX recovery, pre- and post-infusion blood samples for TGA parameters are also drawn.

FIX activity and TGA parameters will also be determined prior to and following a regular prophylactic infusion at 4 additional time points in a 6-month period, **without the requirement of a wash-out period**:

- On 2 occasions, these should be assessed 3 days after a prophylactic infusion, ie, before and after the subsequent prophylactic infusion of BAX326:
  - Last prophylactic infusion approximately 72 hours (3 days) prior to FIX and TGA determination
  - Within 30 minutes prior to regular prophylactic infusion blood sampling for FIX activity and TGA parameters
  - Administration of regular prophylactic infusion of BAX326
  - 30 $\pm$ 5 minutes post-infusion blood sampling for FIX activity and TGA parameters
- On another 2 occasions, these should be assessed 4 days after a prophylactic infusion, ie, before and after the subsequent prophylactic infusion of BAX326:
  - Last prophylactic infusion approximately 96 hours (4 days) prior to FIX and TGA determination
  - Within 30 minutes prior to regular prophylactic infusion blood sampling for FIX activity and TGA parameters
  - Administration of regular prophylactic infusion of BAX326
  - 30 $\pm$ 5 minutes post-infusion blood sampling for FIX activity and TGA parameters

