1.1 Study Objectives

The objectives of this study are:

- To further evaluate safety of BAX326 in terms of investigational product (IP) related adverse events (AEs) as well as clinically significant changes in routine laboratory parameters (hematology/clinical chemistry) and vital signs.
- To further evaluate the hemostatic efficacy of BAX326 in the prevention and routine prophylaxis of acute bleeding episodes using various dose regimens.
- To further evaluate the hemostatic efficacy of BAX326 in the management of acute bleeding episodes.
- To further evaluate the immunogenicity of BAX326 for up to 100 exposure days (EDs) to BAX326.
- To monitor incremental recovery (IR) of BAX326 over time.
- To evaluate changes in health-related quality of life (HR QoL), Patient Activity Level and health resource use.
- Exploratory: To correlate pre-infusion thrombin generation assay (TGA) parameters with pre-infusion FIX levels and spontaneous breakthrough bleeds in a subset of subjects receiving twice weekly standard or modified prophylaxis including pharmacokinetic (PK) tailored prophylaxis.

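### No correlation estimate is planned for pre-infusion TGA against FIX, and the subject-median plot rests on a similarity condition that 3-day, 4-day and wash-out sampling makes effectively unattainable

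*SAP*

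**What the plan says.** SAP 1.1 states the exploratory objective as "To correlate pre-infusion thrombin generation assay (TGA) parameters with pre-infusion FIX levels and spontaneous breakthrough bleeds", in a subset on prophylaxis. Protocol 14.3.3 is looser: "The association of pre-infusion TGA parameters with pre-infusion FIX activity level and spontaneous bleeds during prophylaxis will be explored".

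For TGA against FIX, SAP 11.2 plans three displays:
- "Scatterplots of pre-infusion TGA parameters against pre-infusion FIX level will be presented for each time point".
- By-subject plots, always produced: "To determine the suitability of this analysis, a plot of individual and median pre-infusion TGA parameter values by subject will be provided", with a matching plot for FIX activity.
- A plot of median TGA against "median FIX level for each subject will be presented if pre-infusion values of FIX level and TGA parameters are similar across all time-points".

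Similarity is not defined and is judged from the by-subject plots. The TGA summary tables in SAP 11.2 cover only exposure day 1 (newly recruited subjects) and end of study.

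Protocol 8.1.4 sets the extra sampling: "In approximately 20 subjects receiving twice weekly standard prophylactic infusions of BAX326", four additional occasions within six months. Protocol Table 21.1-1, item 7 gives the timing. Two occasions have "Last prophylactic infusion approximately 72 hours (3 days) prior to FIX and TGA determination", and two have "Last prophylactic infusion approximately 96 hours (4 days) prior to FIX and TGA determination". The same subjects are also sampled at three regular visits after a wash-out of at least 5, preferably 7, days. Under Protocol 11.1.5 and 11.2.3, modified subjects dosed three times weekly are sampled at 2 and 3 days.

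**The concern.** An objective to correlate two measurements calls for an estimate of how strongly they are related and how uncertain that estimate is. None is planned. The one display that sets TGA against FIX using all of a subject's occasions is released only if both are similar across those occasions. Where the interval since the last infusion is varied on purpose, FIX should not be similar. If it were, taking medians would discard the within-subject spread.

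The 3- and 4-day samples also fall outside the summary tables, so in SAP 11.2 they can reach only the plots. Separate scatterplots by time point show differences between subjects at one interval. They do not show how TGA moves within a subject as FIX falls.

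**Working it through.** The documents give no target correlation, sample size or similarity criterion here, so there is no planned figure to reproduce. Two checks follow.

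**1. Can FIX be similar across occasions?**

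Inputs:
- Dose 50 IU/kg twice weekly (SAP 2.1).
- Mean incremental recovery 0.87; median half-life 24.58 h, range 15.83 to 52.34 h (Protocol 6.4.1).
- Sampling at 72 h, 96 h, and 120 to 168 h (Protocol Table 21.1-1, item 7).

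Formula: FIX above baseline = dose × recovery × 2^(−t/half-life), starting from 50 × 0.87 = 43.5 IU/dL.

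| Hours since last infusion | 72 | 96 | 120 | 168 |
|---|---|---|---|---|
| Expected FIX, IU/dL | 5.71 | 2.90 | 1.48 | 0.38 |

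The ratio between two times is 2^(time difference/half-life), so recovery cancels:
- 72 to 96 h: 2^(24/24.58) = 1.97 (2.86 at the shortest half-life, 1.37 at the longest).
- 72 to 120 h: 2^(48/24.58) = 3.87 (8.18 to 1.89).
- 72 to 168 h: 2^(96/24.58) = 15.0 (66.9 to 3.57). With values below 1% set to 0.5%, as SAP section 9 does for descriptive statistics, it is 5.71/0.5 = 11.4.
- Three-times-weekly modified, 48 to 72 h: again 1.97.

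Two refinements:
- An assumed endogenous level of 1.5% gives (5.71 + 1.5)/(0.38 + 1.5) = 3.8 for 72 to 168 h, and (5.71 + 1.5)/(2.90 + 1.5) = 1.64 for 72 to 96 h.
- The previous dose was given 168 h before either trough and adds about 0.38 IU/dL. The 72 to 96 h ratio becomes (5.71 + 0.38)/(2.90 + 0.38) = 1.86.

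Other regimens differ. Once-weekly modified subjects are sampled at exactly 7 days (Protocol 11.1.5), and PK-tailored subjects have TGA only at scheduled visits (Protocol 11.2.2), which follow a wash-out. At a constant interval the expected ratio is 1. If visits vary between 5 and 7 days it can reach 3.87 at the median half-life.

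**2. Would an estimate be informative?**

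The documents give no correlation, so r = 0.5 is assumed. With one pair per subject, the 95% CI is tanh(atanh r ± 1.96/√(n − 3)):
- n = 20: tanh(0.549 ± 1.96/√17) = 0.07 to 0.77.
- n = 40 (the approximate total in Protocol 8.1.4): tanh(0.549 ± 1.96/√37) = 0.22 to 0.70.

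For a within-subject correlation with 20 subjects × 7 occasions (2 + 2 + 3), there are 140 pairs. Degrees of freedom are 140 − 20 − 1 = 119 and the interval is tanh(0.549 ± 1.96/√118) = 0.35 to 0.62. At other assumed values:

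| Assumed r | 20 single pairs | 20 × 7, within subject |
|---|---|---|
| 0.3 | −0.16 to 0.66 | 0.13 to 0.45 |
| 0.7 | 0.37 to 0.87 | 0.60 to 0.78 |

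**The case against.** The strongest reply is that nothing has been breached. The objective is labelled exploratory, Protocol 14.3.3 promises only that the association will be explored, and the SAP is descriptive throughout. The Amendment 6 summary says TGA testing is optional and that numbers per regimen cannot be anticipated. This stands: the SAP does not depart from Protocol 14.3.3, and the point is an improvement in method. It does not supply the quantity that the objective itself names.

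Three stronger readings are tempting, and the documents do not support them:
- That the sampling design rules out the median plot altogether. PK-tailored and once-weekly subjects are sampled only after long intervals, so the condition can hold for them.
- That nothing but per-time-point scatterplots remains. The by-subject plots of TGA and of FIX are unconditional and show every occasion. Withholding the median plot when values vary is also a reasonable safeguard. But the by-subject plots show the two variables separately and do not relate one to the other.
- That the extra visits were added to estimate a within-subject slope. The Amendment 4 summary gives the reason for the added FIX sampling as measuring trough levels and exploring whether they protect against bleeds. It speaks of a potential correlation of TGA, FIX and bleeds, not of a within-subject one.

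The decay model is also simple: one compartment, with no distribution phase. This affects the size of the fall, not its direction.

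**Conclusion.** The point holds in limited form. No estimate of the TGA-FIX correlation is planned. For standard twice-weekly subjects, and modified subjects dosed two or three times weekly, the similarity condition is effectively unattainable. At the median half-life, FIX above baseline changes about 2-fold between the two troughs and about 4- to 15-fold down to wash-out. At the longest half-life quoted, the changes are 1.4-fold, and 1.9- to 3.6-fold. If similarity is judged once over all TGA subjects pooled, it fails whenever these subjects are included; the SAP does not say whether it is judged that way or by regimen.

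The precision figures assume r, full uptake by about 20 subjects, all seven samples from each, and independent residuals within subject. Importance is low because the objective is exploratory.

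**What to change.** In SAP 11.2, keep the plots and add:

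1. Spearman coefficients with 95% CI by time since last infusion (2, 3 or 4 days as the regimen gives, and wash-out). Use one value per subject at each interval so that pairs are independent.
2. One repeated-measures analysis per TGA parameter over all pre-infusion samples during prophylaxis, with a subject effect. For example, regress log TGA on the subject's mean log FIX and on the deviation from that mean. Report the within-subject slope or correlation with 95% CI, and keep the between-subject part separate.
3. A rule for FIX below 1%. Treat it as left-censored, or flag it and repeat the analysis without it. A single 0.5% value could otherwise stand for up to three of seven samples per subject and drive a log-log slope. Dropping those samples also shortens the FIX range, so show both results.
4. If the median plot stays, a definition of similarity and a statement of whether it is judged by regimen.

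Label the results exploratory and report the number of subjects and pairs. The cost is SAP wording and a small amount of programming, with no new samples. If uptake of the optional testing is low, the estimates will be imprecise.

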#### **10.5 Subject Diary**

A subject diary will be provided to each subject or the subject's legally authorized representative:

- At screening/at all the following study visits, ie, every 3 months  $\pm$  1 week, except the study completion/termination visit

The subject diary will be used to record the following information:

- Infusion record of IP (date, time of the infusion, number of units infused, number of vials utilized, lot number, and reason for infusion [bleeding episode, or prophylactic infusion])
- Details of bleeding episodes (site, type, and severity of bleeding) and response to treatment as described in Section 11.3 "Hemostatic Efficacy"
- All AEs will be recorded that do not fall within the provisions of Section 12.3 "[Untoward Medical Occurrences Not Considered Adverse Events](#)".
- Concomitant medications taken (including immunizations) and non-drug therapy
- Drug accountability (number of unused vials of IP remaining in the subject's refrigerator will be recorded, prior to each study visit).

Subjects and/or their legally authorized representatives will be trained on use of the diary. The diary will be returned to the investigator at interval study visits and will serve as source documentation. At each interval study visit as described above, the subject will turn in a single diary and receive a blank one. The subject diary will serve as a source record and remain at the study site. The currently used paper diary may be replaced by an electronic diary.

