### **11.2.2 Pre- and Post-Infusion TGA Parameters Over Time in Subjects Receiving PK-Tailored Prophylaxis**

TGA parameters will be determined pre- and post-infusion of BAX326 at the following visits in all or approximately 20 subjects  $\geq$  12 years and receiving PK-tailored prophylaxis:

- At ED 1 – for transitioning subjects who have undergone a PK study in BAX326 Pivotal, BAX326 Pediatric or BAX 326 Surgery
- At Week 4  $\pm$  1
- At Month 3  $\pm$  1 week
- At Month 6  $\pm$  1 week

---

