**Table 21.1-1**  
**Flow Diagram of Required Procedures for Baxalta Clinical Study 251001**

**8. Study Completion/Termination Visit**

If the subject has accumulated a total of 100 EDs during the course of Studies 250901/251101 and 251001, or BAX326 is licensed in the subject's country, whichever occurs last, this will be the subject's study completion/ termination visit.

The visit must be arranged so that there is a wash-out period of at least 5 days (120 hours), preferably 7 days, from the previous dose of BAX326 and the subject must not be actively bleeding.

Prior to the recovery assessment:

- 1) Review and discuss subject diary
- 2) Record AEs
- 3) Concomitant medication and non-drug therapy use
- 4) Occurrence of target joints
- 5) Collect Health Resource Utilization items
- 6) Physical examination
- 7) Blood draws for:
  - a) Immunology (pre-infusion of IP)
  - b) Hematology and clinical chemistry
- 8) Urine sample for urinalysis
- 9) Assess HR QoL items pre- or post-infusion of BAX326 including Patient Activity Level
- 10) Vital signs within 15 minutes of start of infusion

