**11) Assessment of FIX recovery (and determination of TGA parameters, if applicable)**

- a) Pre-infusion blood draw for FIX activity (and TGA parameters, if applicable) within 0.5 h of start of infusion
- b) Infusion of  $75 \pm 5$  IU/kg BAX326
- c) Post-infusion blood draw for FIX activity (and TGA parameters, if applicable) at  $30 \pm 5$  minutes
- d) Vital signs at  $30 \pm 5$  minutes and 2 h  $\pm 10$  minutes following completion of the infusion

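### The SAP 11.2 box plots of TGA against later spontaneous bleeds do not require the 4 weeks to be observed and do not separate samples by time since the last infusion

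*SAP*

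**What the plan says.** **The plot.** The last paragraph of SAP 11.2 groups pre-infusion TGA values "for subjects who did and who did not experience one or more spontaneous bleeds within 4 weeks after the corresponding pre-infusion TGA sample". It gives no rule for a window that is not fully observed and does not mention sample type or time point. The scatterplots of TGA against factor IX in the same section are to be produced for each time point.

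**Termination-visit samples.** The completion/termination visit in protocol Table 21.1-1 (item 8) includes a "Pre-infusion blood draw for FIX activity (and TGA parameters, if applicable) within 0.5 h of start of infusion". Of the same visit it says: "The visit must be arranged so that there is a wash-out period of at least 5 days (120 hours), preferably 7 days". Protocol 10.5 provides a diary at screening and every later visit "except the study completion/termination visit". Protocol 12.1.1 does not count bleeding episodes as adverse events.

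**Samples during standard twice-weekly prophylaxis.** Protocol 11.2.4 schedules four samples per subject without wash-out, two about 72 h and two about 96 h after the previous infusion. It adds three at regular visits, for which Table 21.1-1 (item 7) states that "there will be a wash-out period of at least 5 days (120 h), preferably 7 days". Once-weekly dosing differs: protocol 11.1.5 sets the regular visit at exactly 7 days, so the visit sample is the trough.

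**Tables.** SAP 11.2 states that "TGA parameters will be summarized using descriptive statistics for exposure day 1 (only applicable for newly recruited subjects") and for end of study. Protocol 11.2.2 also schedules exposure day 1 TGA in the PK-tailored group "for transitioning subjects who have undergone a PK study in BAX326 Pivotal, BAX326 Pediatric or BAX 326 Surgery".

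**The concern.** The exploratory objective is to correlate pre-infusion TGA with factor IX level and with spontaneous breakthrough bleeds on prophylaxis. The bleed comparison needs two things: a known bleed outcome after each sample, and a TGA value that reflects the protection the subject has on the regimen. The plot specification secures neither.

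A termination-visit sample has no planned bleed record afterwards. A program that looks for a bleed in the next 28 days finds none and returns no bleed. These are also wash-out samples, so in a twice-weekly subject they are lower than the usual trough.

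A wash-out value from a regular visit does not describe the following 4 weeks either. The visit itself includes an infusion, after which the usual regimen resumes. Pooling wash-out samples with troughs adds spread that comes from the sampling schedule and not from the subject.

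Both features work against seeing an association if low TGA does go with more bleeding.

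**Working it through.** The plan states no sample size, effect or test for this analysis, so there is no figure of its own to reproduce. The calculations below are illustrations.

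**1. Is any bleed follow-up planned after termination?** No diary is issued at that visit (protocol 10.5). Protocol 12.1.2 follows unresolved adverse events for up to 30 days, but bleeds are not adverse events (12.1.1). The 4 weeks after a termination sample are therefore unobserved by design. SAP 5.2 applies observed-case handling to missing data. An absent bleed record is not a missing value, so that rule does not by itself remove these samples.

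**2. How different are the samples?** Inputs: 50 IU/kg twice weekly (protocol 8.1.1), median half-life 24.58 h and mean incremental recovery 0.87 (protocol 6.4.1), intervals alternating 72 and 96 h (Table 11.2-3), one-exponential decay, no endogenous factor IX. The level is the sum over past doses of 50 × 0.87 × 2^(−t/24.58), with t the hours since each dose.

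| Hours since last dose | Largest terms (%) | Level (%) |
|---|---|---|
| 72 | 5.71 + 0.38 + 0.05 | 6.1 |
| 96 | 2.90 + 0.38 + 0.03 | 3.3 |
| 120 | 1.48 + 0.19 + 0.01 | 1.7 |
| 168 | 0.38 + 0.05 | 0.4 |

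The last two rows take 72 h as the interval before the last dose. With 96 h they become 1.6 and 0.4.

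The trough-to-wash-out ratio runs from 3.31/1.68 = 2.0 to 6.15/0.43 = 14. Subjects with 1-2% endogenous factor IX are eligible:

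- Adding 1% gives 4.31/2.68 = 1.6 to 7.15/1.43 = 5.0.
- Adding 2% gives 5.31/3.68 = 1.4 to 8.15/2.43 = 3.3.

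For descriptive statistics SAP 9 sets factor IX below 1% to 0.5%. With no endogenous factor IX, the largest recorded ratio would be 6.15/0.5 = 12.

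**3. How large is the label error alone?** Let p be the probability of at least one bleed in 28 days, 1 − exp(−rate × 28/365.25), and f the share of plotted samples taken at termination. The share of the no-bleed group truly followed by a bleed is f·p / [(1 − p)(1 − f) + f]. Four troughs, three regular-visit samples and one termination sample give f = 1/8; 1/4 is shown as a higher case.

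| Rate per year | p | f = 1/8 | f = 1/4 |
|---|---|---|---|
| 0.72 (spontaneous bleeds, published study of another recombinant factor IX, protocol 6.1) | 5.4% | 0.7% | 1.4% |
| 4.20 (pivotal mean, all bleeds, used as an upper anchor, protocol 6.4.1) | 27.5% | 4.5% | 8.7% |

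Label error alone is small.

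**4. What if both features act together?** A simulation used log factor IX as a stand-in for TGA, a single-dose decay curve (recovery 0.88), and per subject two samples at 72 h, two at 96 h, three wash-out samples at 120-168 h and one termination wash-out sample forced to no bleed. Assumptions not in the documents: half-life CV 20-30%, recovery spread about 25%, assay noise 0.2 log units, bleed log-rate slope 0.3-0.7 per SD of trough.

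| Samples plotted | Standardised separation (followed troughs only = 1.00) |
|---|---|
| Wash-out and trough pooled, termination left out | 0.69-0.77 |
| All pooled, termination counted as no bleed | 0.19-0.58 |

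In one weak-association scenario the group medians reversed slightly (−0.015 log units).

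**The case against.** A reader might infer that the SAP counts every end-of-study sample as no bleed. It does not say so. It is silent, and an analyst could read the observed-case rule as grounds for dropping them. Termination TGA is also only drawn where applicable. What stands is that nothing in the text excludes these samples, and the literal grouping places them in the no-bleed group.

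Pooling is not stated either. The neighbouring scatterplots are by time point, and the median plots are conditional on values being similar across time points, so separate box plots are not ruled out. The additional visits might also be treated as extra measurements under SAP 5.2. The box-plot sentence itself contains no split.

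A reader might also infer that the 72 and 96 h samples are lost to the bleed analysis. The restriction to exposure day 1 and end of study is written for the tables, not the plots. If it did reach the plots, those samples could not be mixed with wash-out values. The supported point is narrower: the tables omit samples that the protocol schedules.

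The factor IX ratios are not TGA effects, since the documents give no relation between the two, and endogenous factor IX and the quantification limit shrink them. Finally, excluding every wash-out sample would go too far. It would remove the true troughs of once-weekly subjects, and SAP 6.6 counts PK-tailored infusions as on schedule at 6-8 days. These limits are accepted here.

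**Conclusion.** The point holds as a gap in specification with a predictable direction. SAP 11.2 neither requires 28 observed days after a sample nor separates samples by time since last infusion. If termination samples default to no bleed and wash-out samples are pooled with troughs, the contrast would tend to be attenuated. A claim that the plots are certainly misclassified, or that the association will be reversed, is not supported.

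The size is uncertain. Label error alone is about 1% of the no-bleed group at 0.72 bleeds per year. The larger attenuation comes from the two features together and rests on assumed variability and slopes. The pooling concern applies to regimens with intervals shorter than the wash-out, not to once-weekly dosing. The analysis is exploratory, graphical and without a test, and no primary or secondary outcome is touched.

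**What to change.** In SAP 11.2:

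- Include in the box plots only pre-infusion samples followed by 28 days of observed bleed follow-up on the same prophylactic regimen.
- Plot separately (a) samples taken at the subject's own regular dosing interval, including those at about 7 days in once-weekly or PK-tailored subjects, and (b) samples taken after a wash-out longer than that interval.
- Summarise TGA by time since last infusion, so that the scheduled 72 and 96 h samples are reported.
- Reconcile the exposure day 1 restriction with protocol 11.2.2, which schedules that sample for transitioning PK-tailored subjects with a prior PK study.

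The cost is SAP wording and a filter in the program. No new data are needed. The downside is fewer points in each plot.
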